2.1.1 General definitions

Study drug

Novartis will supply the investigational product listed below

- AMG 334 70 mg/1 mL pre-filled syringe
- Matching placebo in 1mL pre-filled syringe, identical in appearance

One injection of AMG 334 70 mg and one of placebo will be administered at each dosing visit. The matching Placebo to AMG 334 pre-filled syringe will have the same appearance as the investigational drug. Each syringe will be packaged individually in double blinded fashion for the DB treatment period. For the open-label treatment period each pre-filled syringe will be packaged individually in open-label fashion. This open-label study treatment will be labeled as AMG334 70 mg.

2.1.1.1 Study dates

eDiary Device Assignment Date

The date on which an eDiary device is assigned to a subject for the first time after completion of initial screening at week -4 visit.

Randomization (Enrollment) Date

Randomization (Enrollment) Date is the date on which a subject is assigned to one of the treatments through IRT in DB period.

First DB IP Dose Date

The first DB IP dose date is the date on which a subject is administered the first dose of IP following randomization, which may be the same day (most of the time) or after the randomization date. For subjects who are randomized but never dosed with double-blind IP after randomization, First DB IP Dose Date is considered missing.

Last DB IP Dose Date

The last DB IP dose date for each subject is defined as the latest date IP is administered during DB period.

First OLE IP Dose Date

The first OLE IP dose date is the date on which a subject is administered the first OLE dose of IP on or after Week 12. The first OLE IP dose date will only be applicable for subjects who enter OLE period.

Last OLE IP Dose Date

The last OLE IP dose date for each subject is defined as the latest date IP is administered during OLE period, which is applicable for subjects who enter OLE period.

Subject-level End of DB Treatment (EOT DB) Date

The end of DB treatment date for each subject is defined as the end of the treatment in DB period. The date will be recorded on the Treatment disposition eCRF page.

Subject-level End of OLE Treatment (EOT OLE) Date

The end of OLE treatment date for each subject is defined as the end of the treatment in OLE period. The date will be recorded on the Open-label Treatment disposition eCRF page.

Subject-level End of Study (EOS) Date

The end of study (EOS) date for each subject is defined as the last date on which the subject participated in the study. The date will be recorded on the Study disposition eCRF page.

2.1.1.2 Study points of reference

Study day

Study Day 1 is defined as the first investigational product (IP) dose date. For subjects who are randomized but not dosed after randomization, the Study Day 1 is defined as the date of randomization.

Study Day is defined as the number of days from Study Day 1.

Before Study Day 1:

Study Day = (Date of Interest – Date of Study Day 1)

On or after Study Day 1:

Study Day = (Date of Interest – Date of Study Day 1) + 1

Therefore the day prior to Study Day 1 is -1.

Baseline

The baseline period for efficacy endpoints collected by the daily eDiary (e.g., monthly migraine days, acute migraine-specific medication days, [REDACTED], ...) is defined as the period between week -4 visit (when eDiary device is dispensed to the subject for daily data capture) and the day prior to study day 1 (study day 1 is not included).

A baseline for PRO [REDACTED], BDI-II, MIDAS) and safety (including C-SSRS) values refers to the last evaluable measurement prior to the first administration of the study drug, irrespective of re-screening. In this case, baseline values will be the values obtained on day 1 (date of first administration of study drug or randomization day if the subject was not dosed after randomization) or on an earlier visit (scheduled or unscheduled) which is the closest to day 1 visit, if the assessment was not done on day 1. In case of multiple assessments on the same day, the first one will be considered for PRO and the latest one for safety; for C-SSRS the first complete assessment performed with the electronic version (“Since last visit” recall period) or supplemental data collected on the CRF page will be used.

Note: Assessments on the day of randomization are assumed to have been taken as per protocol, i.e. if the assessment should be performed before dosing, the assessment will be treated as pre-dose as per protocol. Practically, i.e. that the time part of the date/time entry will be ignored. Exception: In case there is a protocol deviation or a comment that specifically indicates that the assessment has been taken post-dose, the assessment will not be treated as pre-dose.

C-SSRS screening value

Screening value for C-SSRS refers to the last evaluable complete assessment for the recall period “Lifetime” prior or on day 1.

2.1.1.3 Arithmetic calculations

Change from Baseline in Monthly Efficacy Measurement

The change from baseline in monthly efficacy measurement is the monthly efficacy measurement in the monthly interval prior to the given time point minus the baseline monthly efficacy measurement. Please, refer to the monthly intervals for efficacy endpoints defined in [Table 2-2](#). For example, change from baseline in monthly migraine days in the last 4 weeks of the 12-week treatment period will be calculated based on the following:

(Monthly migraine days in the last 4 weeks of the 12-week treatment period) – (monthly migraine days during the baseline period)

If the baseline or post-baseline value is missing, then the change from baseline is set to be missing.

Percent Change from Baseline

The change from baseline divided by baseline and multiplied by 100:

$$(\text{post-baseline} - \text{baseline}) * 100 / \text{baseline}$$

Response rate 50% [REDACTED] will be defined as a decrease from baseline score value of at least 50% [REDACTED]

Duration of Migraine

The duration of migraine in years (migraine with aura or migraine without aura, whichever is earlier) is calculated by the following formula: current age (in years) - age at migraine onset (in years).

If the current age or the age at migraine onset is missing then duration of migraine will be missing.

Duration of exposure to AMG 334

For all calculations of exposure, dose date refers to receiving dose > 0 , but can include partial doses.

The duration of exposure in days for DB Period is computed as min (last DB treatment dose date + 27, EOT visit, cutoff date) – First Dose Date + 1.

The duration of exposure in days for OLE Period is computed as min (last OLE treatment dose date + 27, EOS date) – First OLE Dose date + 1

Compliance with the eDiary

Compliance to eDiary at each month is calculated as

- (Number of eDiary entered in baseline period or between IP doses/28days)*100% if the number of actual days in Baseline period or between IP doses interval is ≤ 28 days

- (Number of eDiary entered in baseline period or between IP doses/ number of actual days in Baseline period or between IP doses interval)*100% if the number of actual days in Baseline period or between IP doses interval is > 28 days

The protocol requirement is 80% compliance in 28 days at baseline period. That means minimum 23 diaries must be completed within 28 days.

2.1.2 Disease characteristics

Treatment Failure of Prior Migraine Prophylactic Medications

Treatment failure of prior migraine prophylactic medications is determined by “Reason for ending medication” as “Lack of efficacy” (with therapeutic dose) or “Lack of tolerability” in the Prior Migraine Prophylactic Medication eCRF page. Those medications are classified in 13 categories (as per protocol section 6.2.2):

- Category 1: Divalproex sodium, sodium valproate
- Category 2: Topiramate
- Category 3: Beta blockers (for example: atenolol, bisoprolol, metoprolol, nadolol, nebivolol, pindolol, propranolol, timolol)
- Category 4: Tricyclic antidepressants (for example: amitriptyline, nortriptyline, protriptyline)
- Category 5: Flunarizine, verapamil, cinnarizine
- Category 6: Serotonin-norepinephrine reuptake inhibitors (for example: venlafaxine, desvenlafaxine, duloxetine, milnacipran)
- Category 7: Botulinum toxin
- Category 8: Lisinopril, candesartan
- Category 9: Pregabalin, gabapentin
- Category 10: Zonisamide
- Category 11: Memantine
- Category 12: Pizotifen
- Category 13: Cao Wu Jia Su Pian, Du Liang Ruan Jiao Nang

For medications entered as free text, categorisation will be provided by clinical team prior DBL. The number of failed prior prophylactic treatments is the number of categories with at least one failed prior migraine prophylactic medication.

2.1.3 Visit and analysis windows

Visit window for DB period

Since the actual visit for a subject may not exactly coincide with their targeted visit date, the actual visit date is mapped to a study visit.

The next study day window will be utilized to define study visit for data captured in DB period - lab, vital signs, ECG, C-SSRS and some PROs collected during office visits ([REDACTED] BDI-II, mMIDAS) before dose is administered.

Table 2-2 Study Visit Windows

Study visit	Target Day	Study Day
Baseline	See baseline assessment of the Study (Section 2.1.1.2 , baseline definition)	
Week 4	28	16 - 43
Week 8	56	44 - 71
Week 12	84	72 - 99
Safety follow-up (for safety endpoints)	Safety follow-up should be excluded from the analysis visit windows described above and summarized under 'safety follow-up visit' for safety analyses only. Target day: last IP dose date + 12 weeks	

For safety endpoints (like lab, vital signs) except ECG, when assessment value for scheduled visit and unscheduled visit are both present within the same analysis window, scheduled visit value should be used. Unscheduled visit will only be used when there is no measurement from the scheduled visit in the defined window. In case of multiple assessment values among the same type of visit (ie, scheduled vs. unscheduled) within the same analysis window, the closest to the scheduled visit day will be used. In case of equal distances (e.g same day), the latest assessment value will be used. The exception is an assessment at early study withdrawal visits along with another assessment within a window. In such cases, the early-withdrawal assessment will be used. For ECG, the same strategy will be applied except that no prioritization of scheduled vs unscheduled visit will be made.

In case of multiple assessments on the same day for PROs (including C-SSRS), the first assessment will be used. For C-SSRS, the first complete assessment performed with the electronic version ("Since last visit" recall period) or supplemental data collected on the CRF page will be used. In case of multiple days with assessments within an analysis window (for post-baseline visit) for PROs and C-SSRS, the day the closest to the scheduled visit day will be used.

Monthly Interval for Efficacy Endpoints (from eDiary)

Monthly efficacy measurements will be calculated based on the subject's monthly investigational product (IP) dosing schedule defined below using eDiary data collected from beginning of the baseline period (Week -4 visit) up to the End of Treatment in DB period (Week 12 visit).

Table 2-3 Study Intervals for Efficacy Endpoints

Study Phase	Assessment Time point	Interval Based on Dose Dates	
		Start date	End date
Baseline Period	Baseline	From eDiary device assignment date (or Week -4 visit)	Day prior to study day 1
DB Period	Week 4	Study Day 1	
• Week 4 dose date-1• Study day 28 if Week 4 dose is not received (either missed or IP discontinued prior to Week 4) 
Note: if day 1 dose is the last IP dose subject received, the rest of monthly assessments during treatment period will be calculated based on consecutive 28-day interval beginning on study day 29 (ie, 29-56 for week 8, 57-84 for week 12)

	Week 8	
• Week 4 dose dateStudy day 29 if Week 4 dose is not received (either missed or IP discontinued prior to Week 4)	
• Week 8 dose date-1Study day 56 if Week 8 dose is not received (either missed or IP discontinued prior to Week 8)
	Week 12	
• Week 8 dose dateStudy day 57 if Week 8 dose is not received (either missed or IP discontinued prior to Week 8)	
MIN (Study day 84, EoS) if Week 8 dose is not received
 
MIN (Week 8 dose date + 28, EoS) if week 8 dose is received

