#### **8.4.4      Prospective suicidality assessment**

The C-SSRS is a questionnaire that prospectively assesses Suicidal Ideation and Suicidal Behavior. The C-SSRS must be administered at each visit of the double-blind treatment period, including unscheduled visits.

A validated version of the electronic Columbia Suicide Severity Rating Scale eC-SSRS will be used to capture self-reported eC-SSRS data via a web-based interactive response system and via a phone system (both interchangeable). The eC-SSRS uses a detailed branched logic algorithm to perform the eC-SSRS subject interview, evaluating each subject's suicidality ideation and behavior in a consistent manner. At the conclusion of each assessment, a detailed eC-SSRS Findings Report will be available on the vendor portal. If the system assesses the subject as having positive suicidal signs, the investigator will be immediately notified by either email and via telephone.

If, at any time after screening and/or baseline, the score is “yes” on item 4 or item 5 of the Suicidal Ideation section of the C-SSRS or “yes” on any item of the Suicidal Behavior section, the subject must be referred to a mental health care professional for further assessment and/or treatment. The decision on whether the study treatment should be discontinued is to be taken by the investigator in consultation with the mental health professional to whom the subject is referred.

In addition, all life-threatening events must be reported as SAEs. For example, if a subject answers “yes” to one of the questions in the Suicidal Behavior section, an SAE must be reported if the event was life-threatening. All events of “Non-Suicidal Self-Injurious Behavior” (question also included in the Suicidal Behavior section) should be reported as AEs and assigned the appropriate severity grade.

All SAEs relating to suicidal behavior must be reviewed by the safety physician.

During the **COVID-19 pandemic** that limits or prevents on-site study visits, the eC-SSRS may still be collected via a web-based interactive response system or via a phone system (both interchangeable). In this latter case, the dialing number will be temporarily kept by the vendor.

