### **Laboratory data**

The mean and change from baseline values of laboratory data will be summarized over time. Shift tables of the most extreme post-baseline value from baseline will be tabulated.

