2.7.4.3 Columbia-Suicide Severity Rating Scale (C-SSRS)

C-SSRS will be collected during DB period and safety follow-up period.

The number and percentage of subjects reporting any suicidal ideation or any suicidal behavior will be summarized descriptively by treatment group and by visit.

Shift table of C-SSRS maximum severity of suicidal ideation/behavior compared to baseline will be provided by treatment group by visit.

No statistical testing will be performed on C-SSRS.

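### The nearest-day window rule for the C-SSRS, combined with by-visit-only tables, can leave a positive unscheduled or early End of Treatment result out of the suicidality counts

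*SAP*

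**What the plan says.** Collection is broad. Protocol 8.4.4 states: "The C-SSRS must be administered at each visit of the double-blind treatment period, including unscheduled visits". Protocol 10.2.2 and SAP 2.1.4.2 also require the scale at unplanned or unscheduled visits.

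Analysis is narrower. SAP 2.1.3 names the C-SSRS among the data to be windowed: "The next study day window will be utilized to define study visit for data captured in DB period - lab, vital signs, ECG, C-SSRS". Table 2-2 sets the windows at Days 16-43 (target 28), 44-71 (target 56) and 72-99 (target 84). Two rules then reduce each window to one assessment:

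- Across days: "for PROs and C-SSRS, the day the closest to the scheduled visit day will be used".
- Within a day: "In case of multiple assessments on the same day for PROs (including C-SSRS), the first assessment will be used". For the C-SSRS this is refined to the first complete electronic assessment or supplemental CRF data.

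Baseline cannot absorb Days 2-15, because under SAP 2.1.1.2 it "refers to the last evaluable measurement prior to the first administration of the study drug, irrespective of re-screening". The safety follow-up visit cannot absorb them either: "Safety follow-up should be excluded from the analysis visit windows described above".

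SAP 2.7.4.3 plans two C-SSRS outputs. The first reads: "The number and percentage of subjects reporting any suicidal ideation or any suicidal behavior will be summarized descriptively by treatment group and by visit". The second is a shift table of maximum severity against baseline, again by treatment group and visit. No summary at any time post-baseline is named.

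**The concern.** Choosing the value nearest the target day is reasonable for a by-visit mean. For the question of whether a subject ever reported suicidal ideation or behavior, it can discard the one record that answers yes. Dropping assessments from such a count can lower it but cannot raise it.

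Two situations are exposed. In the first, an unscheduled positive shares a window with a scheduled negative that lies closer to target. In the second, the assessment falls on Days 2-15. That can happen at an unscheduled visit, or when a subject stops early and is unwilling to attend further follow-up visits; Protocol 9.1.1 then asks for the End of Treatment assessments as soon as possible.

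The next scheduled form need not repair the loss. Post-baseline forms use a since-last-visit recall, so a finding that has resolved by then may not be recorded again. At stake is whether the suicidality tables count every subject with a positive result.

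**Working it through.** The plan states no figure to reproduce. The check applies the stated rules to each possible day of one unscheduled assessment.

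**Inputs**

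- Windows and targets: SAP Table 2-2.
- Selection rule: SAP 2.1.3.
- Visit tolerance of 5 days either way: Protocol 6.7.2, for dosing visits.
- Assumption: the scheduled visit day in the rule means the Table 2-2 target day.

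**Step 1, coverage.** Each window is 28 days wide, so 3 × 28 = 84 days are mapped. Days 2-99 are 98 days, so 98 − 84 = 14 days (Days 2-15) map to nothing.

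**Step 2, worked example.** The scheduled C-SSRS on Day 28 is negative and an unscheduled one on Day 40 is positive. Both lie in Days 16-43. The distances to target are |28 − 28| = 0 and |40 − 28| = 12, so Day 28 is used and Day 40 is not.

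**Step 3, all days.** Suppose all three scheduled assessments are done, each k days from target. That leaves 98 − 3 = 95 other days, of which 81 lie in a window and 14 do not. An unscheduled day d in a window with target t is used only if |d − t| < k, which gives 2k − 1 days per window for k ≥ 1 and none for k = 0.

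| Scheduled assessments on Days | Unmapped | In window, not used | Not used, of 95 |
|---|---|---|---|
| 28, 56, 84 (k = 0) | 14 | 81 | 95 |
| 29, 57, 85 (k = 1) | 14 | 81 − 3×1 = 78 | 92 |
| 33, 61, 89 (k = 5, late) | 14 | 81 − 3×9 = 54 | 68 |
| 23, 51, 79 (k = 5, early) | 14 | 81 − 3×9 = 54 | 68 |

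The SAP gives no rule for two C-SSRS days equally far from target. Ties are counted here as not used. Deciding them the other way returns one day per window, giving 89 for k = 1 and 65 for k = 5.

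**Step 4, missing scheduled assessment.** A lone unscheduled assessment inside a window is then used. One on Days 2-15 is still unmapped.

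**Step 5, possible remedies.** Starting the Week 4 window at Day 2 places Days 2-15 at distances 13 to 26 from target. All of these exceed 5, so with the Week 4 assessment done within 5 days of target the change recovers none of them. A worst-result summary over all post-baseline assessments leaves out 0 of 95 days.

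**The case against.** The strongest reply is that little depends on these tables. The C-SSRS is not an endpoint in Protocol Table 2-1, is not among the safety variables in Protocol 12.5.2 and is not in the interim read-out of SAP 2.12.2. SAP 2.7.4.3 excludes testing. Individual subjects are handled outside the tables: the investigator is alerted, referral is mandatory for defined responses, life-threatening events are SAEs and non-suicidal self-injury is an AE. SAP 2.1 also provides in general for listings of data of interest. All of this stands and limits the weight of the point. It does not close the gap: ideation that is not life-threatening has no stated automatic route to an AE, and a listing does not correct a count.

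Several stronger readings are tempting but unsupported:

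- *The event is lost from every C-SSRS table.* Maximum severity in the shift table could mean the worst result within the window, which would rescue Day 40. That reading conflicts with the one-day rule, leaves the table by visit and still misses Days 2-15. The SAP should say which is meant.
- *The rule targets unscheduled or positive results.* For the C-SSRS it selects by distance, not by visit type or result. The ranking of scheduled above unscheduled is written for other safety data such as labs and vital signs.
- *The 14 unmapped days measure the share of assessments lost.* No C-SSRS is scheduled in them, and subjects willing to return have their End of Treatment visit at the next 4-weekly date, which normally falls inside a window.
- *Day 56 cannot recapture a Day 40 event.* The documents do not define which visit anchors the recall, and a persisting finding could be reported again.
- *The same fault defeats the lab and vital-sign tables.* Protocol 12.5.2 says "Shift tables of the most extreme post-baseline value from baseline will be tabulated", but neither document says that those tables use windowed values. SAP 2.7.4.2 counts vital-sign abnormalities at any post-baseline visit. SAP 2.7.3 plans liver-abnormality incidence without by-visit wording and lists notable values.

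**Conclusion.** The point holds as a modest safety-reporting correction. As written, SAP 2.1.3 and 2.7.4.3 together allow a positive C-SSRS from an unscheduled visit, or from an early End of Treatment visit on Days 2-15, to be absent from the by-visit counts. With all scheduled assessments done, an unscheduled result goes unused on 68 to 95 of the 95 other days, depending on how close the scheduled visits are to target (65 at the lowest if ties are decided the other way).

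Those figures describe the rule, not expected losses. Neither document gives a rate of positive C-SSRS results or of unscheduled visits, so the number of subjects affected cannot be estimated. The conclusion assumes that the Table 2-2 targets are the scheduled visit days, and that the table shells, which are not in the documents, add no output for any time post-baseline.

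**What to change.** In SAP 2.7.4.3, add by treatment arm a subject-level summary of suicidal ideation and behavior at any time post-baseline, with a matching shift from baseline. Base both on the worst result over all post-baseline assessments: scheduled, unscheduled and early-withdrawal, including Days 2-15. State there, with a cross-reference in 2.1.3, that the nearest-day and first-of-day rules govern only the by-visit displays. Say whether maximum severity in the by-visit shift table is taken within the selected assessment or across the window. Widening the Week 4 window alone is not a substitute.

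The cost is SAP wording and minor programming, using data already collected. Reported counts may be slightly higher.
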